5.4 Demographic Variables

Demographic variables include patient's age, gender and race/ethnicity which will be collected at screening.

5.5 Medical History

Medical history will include all active conditions, and any condition diagnosed within the prior 10 years that are considered clinically significant by the investigator. Details regarding the disease for which the subject has enrolled in this study will be recorded separately and not listed as medical history.

5.6 Clinical Assessments

Physical examinations will be done at baseline and other time points to assess the general appearance, skin, head and neck, lymph nodes, thyroid, musculoskeletal/extremities, cardiovascular, respiratory, abdomen and neurological characteristics of the patient. The result of the physical examination is recorded as normal, abnormal (clinically significant or not clinically significant) or not done. Clinically significant abnormal findings should be recorded as medical history.

Vital signs including height, weight, blood pressure, body temperature, pulse and respiratory rate will be measured as indicated in assessment schedule. Vital signs may be assessed at any time during the visit; however, supine blood pressure and

pulse should be measured after 10 minutes rest. Height will be measured at initial screening visit only.

Performance status will be assessed according to ECOG (Eastern Cooperative Oncology Group) criteria as follows:

- 0 Fully active, able to carry on all pre-disease activities without restriction
- 1 Restricted in physically strenuous activity but ambulatory and able to carry out work of a light or sedentary nature. For example, light housework, office work
- 2 Ambulatory and capable of all self-care but unable to carry out any work activities. Up and about more than 50% of waking hours
- 3 Capable of only limited self-care, confined to bed or chair 50% or more of waking hours
- 4 Completely disabled. Cannot carry on any self-care. Totally confined to bed or chair
- 5 Death

5.7 Laboratory Evaluations

The following laboratory variables will be measured in the study at designated time points in Table 2:

- Biochemistry: Sodium [Na], potassium [K], chloride [Cl], bicarbonate [CO₂], Uric Acid, calcium, phosphate, glucose), Alanine aminotransferase (ALT), Aspartate aminotransferase (AST), alkaline phosphatase, albumin, Lactate dehydrogenase (LDH), total bilirubin, direct bilirubin (If total bilirubin is elevated above the upper limit of normal)), total protein, magnesium and Blood Urea Nitrogen
- Haematology: White blood cell count (WBC) with differential (to include neutrophils, lymphocytes, monocytes, eosinophils, basophils), red blood cell (RBC) count haemoglobin (Hgb), haematocrit (Hct), Absolute neutrophil count (ANC), Absolute lymphocyte count (ALC) and platelet count.
- Coagulation: PT/INR and aPTT
- Urinalysis: Macroscopic assessment of the amount of protein, glucose, white blood cells and blood if they are present (levels should be recorded

if available) and microscopic analysis should be performed if an abnormality is noted.

- Pregnancy test for patients of child bearing potential (If urine pregnancy results cannot be confirmed as negative, a serum pregnancy test will be required). Serum β -human chorionic gonadotropin (β -hCG) for patients of child bearing potential
- Thyroid: Total triiodothyronine (T3), Free thyroxine (FT4), Thyroid stimulating hormone (TSH)
- Tumour Markers for CUP +/- any serum markers deemed to be relevant to disease monitoring, e.g. PSA, b-HCG, CEA, Ca19.9, Ca125, Ca153, AFP, NSE, SCC, S100, and Chromogranin A and B.
- ‡ If considered standard of care in your region.

Laboratory values that have changed significantly from baseline and are considered to be of clinical concern will be recorded as an adverse event and followed up as appropriate.

5.8 Prior and Concomitant Medications Review

Prior Medications - include prior medication use, including any protocol-specified washout requirement, and prior medication taken by the subject within 28 days before starting the trial. Treatment for the disease for which the subject has enrolled in this study will be recorded separately and not listed as a prior medication

Concomitant Medications - medications, if any, which are taken by the subject during the trial and 30 days after the last dose of trial treatment. All medications related to reportable SAEs and ECIs will be recorded as defined in Section 7 of the protocol.

The following details will be collected: drug name, reason for therapy, therapy dosage / units, frequency of therapy, route of administration, start and end date of therapy.

5.9 Disease Details and Treatments

Prior Cancer Treatments - include systemic treatments, radiation and surgeries.

Post Study Anti-Cancer Therapy Status - all new anti-neoplastic therapy initiated after the last dose of trial treatment. If a subject initiates a new anti-cancer therapy within 30 days after the last dose of trial treatment, the 30 day Safety Follow-up visit must occur before the first dose of the new therapy. Once new anti-cancer therapy has been initiated the subject will move into survival follow-up.

Treatment Compliance - is detailed record of the date and time of administration and drug dose all study treatment that are captured in the patient diary. The number of missed or delayed doses will be reported for each patient and compliance will be reported as the percentage of treatment delays.

5.10 Exploratory Variables

Exploratory variables include genomic biomarkers predictive of immune response to Pembrolizumab. Genomic sequencing will be done within the 100K-genome project, the data from which can be linked to this and other CUP trials. This is not costed in this application and the analysis will not be included in this statistical analysis plan.

6 Statistical Methodology

The study data will be summarised using standard descriptive methods by cohort and as combined data. Histograms and box-plots will be used to assess the distributional assumptions and to check for possible outliers. Mathematical transformations will be applied, where appropriate, in order to render variables normally distributed. Continuous variables that follow an approximately normal distribution will be summarised using the mean and standard deviation (StDev). Skewed continuous variables will be summarised using the median and inter-quartile range (IQR). Categorical variables (binary, ordered and multinomial) will be presented in terms of frequencies and percentages.

The primary outcome and secondary outcome will be tested using a two-tailed hypothesis test with a 5% significant level.

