3.5 Sample Size

1) In the first cohort 20 second-line (or more) patients will be accrued; if no responses or benefit is observed in 20 assessable patients, accrual of the whole trial will stop at this point. “Assessable” is defined as patients who have had at least 2 cycles of Pembrolizumab and are assessable for response at a minimum of 6 weeks post-study start.

2) The study statistics were originally modelled on the UK CUP-ONE trial based on the primary study endpoint of response in cohort 2.

An interim futility analysis was originally pre-planned after recruiting 24 (out of 57) patients in Cohort 2 and a final analysis after 77 participants completed the study (20 for Cohort 1 and 57 for Cohort 2). ≥1 documented response in Cohort 1 was achieved in May 2020, enabling Cohort 2 to open and Cohort 1 to close once sufficient evaluable participants had been enrolled. Due to the unexpected challenges recruiting study participants outlined in the Trial Summary and sections 1.3.1 and 3.1, particularly for Cohort 2, Cohort 1 was reopened and expanded and the initial version 7.0 of the protocol has formally closed Cohort 2 with approval from the TMG, MSD and combined

TSC/IDMC. Cohort 1 (pre-treated patients) remains a crucial area of unmet need with no standard of care treatment existing.

The sample size has thus been recalculated to accommodate the shift of focus to assessing PFS and OS in Cohort 1 and complete removal of Cohort 2. The sample sizes were recalculated based on the Brookmeyer-Crowley test for median survival time (Brookmeyer R and Crowley JJ. A confidence interval for the median survival time. Biometrics. 1982: 38, 29-41).

Assuming a historic null PFS of 2 months and an alternative PFS of 4 months, the minimum required sample size to determine the median PFS for the study cohort is 46 (at 0.05 level of significance, one-sided, 90% power). For the OS, assuming a null OS of 4 months and an alternative OS of 7 months, the required minimum sample size is 67 with the same level of significance and power. Therefore, the final sample size needed to determine both the median PFS and OS is 67 (the higher sample size). In the event that this sample size will be difficult to recruit within the additional accrual period of 12 months, a sample size of 31 will still be able determine the median PFS and 45 the median OS with a power of 80%.

Power	Null Median Survival	Alternative Median Survival	Min N
0.80	2 months PFS	4 months	31
0.90	2 months	4 months	46

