0.80	4 months OS	6 months	83
0.80	4 months	7 months	45
0.90	4 months	6 months	122
0.90	4 months	7 months	67

The study will therefore aim to recruit between 31 and 67 patients to Cohort 1 within the allotted study period. This sample size range is estimated to have a power of 80% to 90% in determining the PFS and/or the OS of the study cohort.

As for DCR, the minimum range of this sample size (i.e. 31) would require ≥ 10 DCR to recommend Pembrolizumab for further evaluation, assuming an unacceptable DCR of $\leq 20\%$ (P0) vs the desired rate of $\geq 40\%$ (P1). This Fleming single-stage design would provide a one-sided alpha of 8% and a power of 86%. Different simulations for the minimum DCR needed ($H_0: P \leq 0.2$ vs $H_1: P \geq 0.4$) given a one-sided alpha $\leq 10\%$ and power $\geq 80\%$ are presented below:

Power	N	Alpha	Minimum DCR needed
0.80	35	0.03	12
0.86	31	0.08	10
0.90	47	0.04	15
0.91	42	0.06	13
0.91	36	0.09	11

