6.3 Primary Efficacy Analysis

The overall response rate will be calculated as the proportion of patients who have a complete response (CR) or partial response (PR) to treatment as assessed by the objective tumour response criteria: RECIST v1.1 **or** immune-related (irRECIST). The response rate and its 95% confidence interval (CI) will be presented for each cohort. As previously described, the response rate is the primary efficacy variable that will be used to decide whether the study will stop or continue accrual in both cohorts.

Disease Control Rate (DCR) will be calculated for each cohort as the proportion of patients in whom the best overall response is determined as complete response (CR), partial response (PR) or stable disease (SD) for at least 12 weeks in either RECIST **or** irRECIST criteria.

The Overall Survival (OS) and Progression Free Survival (PFS) will be summarized descriptively using the median and Kaplan-Meier graph for each cohort.

The Quality of Life (QOL) in each cohort will be assessed using mean or median scores from the EORTC QLQ-C30 (version 3) questionnaire administered at baseline, after 3 months and then at discontinuation of study treatment. The QOL scores between visit dates will be compared using Repeated Measures ANOVA or Friedman's Test on the per-protocol population who completed the baseline and at least one follow-up QoL assessment. The type of statistical test to be used will depend on the characteristic of the data distribution. Adjustment for multiple testing will be applied. The Tukey post-hoc method or the Wilcoxon signed-rank test will be used for pairwise comparisons. Profile plots and longitudinal plots will also be presented.

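### PFS, OS and DCR are sized on one-sided tests, but SAP section 6 prescribes two-tailed 5% tests and SAP 6.3 states no test for PFS or OS

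*SAP*

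**What the plan says.** **Sizing.** SAP 3.5: "The sample sizes were recalculated based on the Brookmeyer-Crowley test for median survival time". The PFS calculation (null median 2 months, alternative 4) is made "at 0.05 level of significance, one-sided, 90% power" and gives 46. OS (null 4, alternative 7) takes the same level and power and gives 67. The fallback sizes at 80% power are 31 for PFS and 45 for OS. Protocol 8.2 carries the same text and table. SAP 3.5 adds a Fleming single-stage rule for DCR, 20% against 40%. At N=31 it asks for at least 10 patients with disease control, which "would provide a one-sided alpha of 8% and a power of 86" per cent. The table that follows allows a one-sided alpha of up to 10%.

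**Analysis.** The opening text of SAP section 6 (Statistical Methodology) says: "The primary outcome and secondary outcome will be tested using a two-tailed hypothesis test with a 5% significant level". SAP 6.3 says that OS and PFS "will be summarized descriptively using the median and Kaplan-Meier graph for each cohort". SAP 5.1 promises a 95% confidence interval for median PFS and gives none for OS. Section 6 nowhere mentions the null medians of 2 and 4 months or the null DCR of 20%.

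**The concern.** The same endpoints carry three instructions in one current document: one-sided in the sizing, two-tailed in the general methods, and descriptive in the efficacy section. A two-tailed 5% test leaves 2.5% in the only direction of interest, so the 80% and 90% powers, and with them the 31-67 range, rest on a more lenient test than the one prescribed.

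The trial is open-label and single-arm. If the lower limit for median OS clears 4 months at one-sided 5% but not at 2.5%, the result is positive or negative according to which section is quoted. For DCR, 10 of 31 meets the rule in 3.5 for recommending further evaluation but cannot reject the null under section 6. SAP 3.5 says that the sample size was recalculated because the focus moved to PFS and OS, so the endpoints that justify N are the ones with no decision rule in the analysis section.

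**Working it through.** **Inputs (SAP 3.5; protocol 8.2 agrees for PFS and OS).** PFS medians 2 v 4 months, N=31 (80%) and 46 (90%). OS medians 4 v 7, N=45 and 67; also 4 v 6, N=83 and 122. DCR 20% v 40%.

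**Assumptions (mine; the documents state neither).** Exponential survival, and no censoring before the null median. The Brookmeyer-Crowley test compares survival at the null median m0 with 0.5. Under the alternative median m1, that survival is p1 = 0.5^(m0/m1): 0.7071 for 2 v 4 and 0.6730 for 4 v 7.

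**Two normal approximations**, with z = 1.645 (one-sided 5%) or 1.960 (two-sided 5%):

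- Identity scale: power = Φ{[(p1 − 0.5)√n − 0.5z] / √(p1(1 − p1))}
- Log-log scale: power = Φ{[ln(m1/m0)√n − z·s0] / s1}, with s0 = 1/ln 2 = 1.4427 and s1 = √((1 − p1)/p1) / |ln p1|, which is 1.857 for 2 v 4 and 1.760 for 4 v 7

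**Reproducing the plan.** One-sided, the log-log formula gives 78.8% (PFS 31), 89.5% (PFS 46), 78.4% (OS 45), 89.5% (OS 67), 78.7% (4 v 6, N=83) and 89.8% (4 v 6, N=122), all within about two points of the stated figures. The identity formula fits the 90% rows (90.0% at PFS 46, 89.7% at OS 67) but falls short in the 80% rows (76.6% at PFS 31, 76.4% at OS 45). No two-sided 5% variant tried reproduces the table as a whole. The sizes are therefore one-sided, including the 80% rows, where the text does not repeat the word.

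**Power at two-sided 5%.** Example, PFS N=31, √31 = 5.568:

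- Identity: (0.2071 × 5.568 − 0.5 × 1.960) / 0.4551 = 0.380, power 64.8%
- Log-log: (0.6931 × 5.568 − 1.960 × 1.4427) / 1.857 = 0.556, power 71.1%

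| Row | Stated | One-sided, identity / log-log | Two-sided, identity / log-log |
|---|---|---|---|
| PFS N=31 | 80% | 76.6 / 78.8 | 64.8 / 71.1 |
| OS N=45 | 80% | 76.4 / 78.4 | 65.0 / 70.1 |
| PFS N=46 | 90% | 90.0 / 89.5 | 82.5 / 84.3 |
| OS N=67 | 90% | 89.7 / 89.5 | 82.3 / 84.0 |
| PFS N=67 | not given | 97.2 / 96.2 | 94.2 / 93.7 |

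**N for 90% power.** On the identity scale, n = {[0.5z + 1.282√(p1(1 − p1))] / (p1 − 0.5)}². One-sided this gives 46.1 (PFS) and 67.8 (OS), against the stated 46 and 67. Two-sided it gives 57.0 and 83.6. The log-log formula gives 57 and 83 two-sided. OS at 90% two-sided therefore needs about 83-84 patients, above the maximum of 67.

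**DCR, exact binomial.** Alpha = P(Bin(N, 0.2) ≥ r) and power = P(Bin(N, 0.4) ≥ r).

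| N | r in SAP | Stated alpha | Exact alpha | Power at r | Smallest r with tail ≤ 0.025 | Power at that r |
|---|---|---|---|---|---|---|
| 31 | 10 | 0.08 | 0.0746 | 85.7% | 12 (tail 0.0127) | 62.5% |
| 35 | 12 | 0.03 | 0.0344 | 80.5% | 13 | 69.4% |
| 36 | 11 | 0.09 | 0.0889 | 91.0% | 13 | 73.9% |
| 42 | 13 | 0.06 | 0.0621 | 91.4% | 15 | 76.4% |
| 47 | 15 | 0.04 | 0.0366 | 90.1% | 16 | 83.7% |

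All five upper tails (0.034-0.089) exceed 0.025. The stated 8% at N=31 is 7.46% exactly, a small rounding matter.

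**The case against.** **Effect size.** Setting 65% against a stated 80% overstates the effect of sidedness, because the identity formula gives only 76-77% one-sided in those rows. Like for like, PFS at N=31 falls from 77% to 65%, or from 79% to 71% on the log-log scale. This stands, and is why a range is given. It also stands that the loss is worst at the fallback sizes. A reader might infer that PFS is under-powered at full recruitment; at N=67 it keeps about 94% two-sided.

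**Are the powered tests never done?** A reader might infer this from SAP 6.3. The documents do not support it in general. Section 6 says the primary outcome will be tested, 3.5 names the method and the null medians, and DCR has an explicit cut-off in 3.5. The 95% interval for median PFS would act as a two-sided 5% test if its lower limit were compared with 2 months. What remains is narrower: no such comparison is stated for PFS, OS has neither test nor interval in the analysis sections, and the DCR rule is not carried into 6.3.

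**Scope of the two-tailed sentence.** It speaks of a single primary outcome, and SAP 6.3 calls response rate the primary efficacy variable, so it might not be meant for PFS, OS and DCR. But SAP 2.1 and 5.1 place all three under the primary heading, and section 6 makes no exception. On the narrow reading, PFS and OS would have no test in section 6 at all, which leaves the gap open.

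**Importance.** The trial is described as hypothesis-generating, and estimates with intervals can be read under either convention. That is fair, but SAP 3.5 still attaches a recommendation to a DCR cut-off and claims 80-90% power for PFS and OS, so the level has to be settled.

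**Conclusion.** The conflict is real, and nothing in the protocol or SAP reconciles it. The powers and DCR cut-offs in SAP 3.5 do not belong to the test that section 6 prescribes, and the PFS and OS decision rules are missing from SAP 6.3.

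Under two-sided 5% testing, power is about 65-71% instead of 80% (PFS N=31, OS N=45) and about 82-84% instead of 90% (PFS N=46, OS N=67). PFS at N=67 stays at about 94%. These figures rest on exponential survival and no early censoring. Using the alternative variance on the identity scale shifts them slightly, to 70-72% and 86-87%. The DCR result needs no survival assumption: no tabulated cut-off suffices at two-tailed 5%, and at N=31 the requirement rises from 10 to 12 with power 62% instead of 86%.

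The documents do not show that the trial is under-powered as a whole or that no test will be done. They show that the level, the sidedness and the PFS and OS rules are left open to choice after the data are seen.

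**What to change.** Before database lock, choose one of two routes; either resolves the conflict.

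- **(a) One-sided.** Replace the two-tailed sentence in SAP section 6 with one-sided tests that match 3.5: 5% for PFS and OS, and one stated alpha ceiling for DCR. Give the exact DCR cut-off for whatever N from 31 to 67 is reached; the present table covers only 31, 35, 36, 42 and 47, at alphas from 3% to 9%.
- **(b) Two-tailed 5%.** Keep the sentence, and restate the PFS and OS powers and the DCR cut-offs, again for every N from 31 to 67.

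Under either route, state in SAP 6.3 that the null is rejected if the lower Brookmeyer-Crowley limit at the chosen level exceeds 2 months (PFS) or 4 months (OS), refer there to the DCR rule, and report a confidence interval for median OS. The 95% intervals can stay for estimation; under (a), add the one-sided 95% lower limit.

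The cost is a short SAP revision and a table of DCR cut-offs, with no new data and no burden on patients. Route (a) openly adopts the more lenient standard; under (b) the stated powers become less favourable.

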6.1 Patient Flow

Details about patient screening, enrolment and assessment are provided in the following diagram:

CUP Patient Identification

- Potentially eligible patients identified at Local CUP or specialist CUP MDT or in clinic suitable for conventional first-line chemotherapy
- Progression or intolerant of first or more lines of conventional chemotherapy potentially eligible

Patient Consent and Screening

- Patients considered potentially eligible provided with Patient Information Sheet
- Patient Informed Consent
- Screening assessments

Registration (n=31-67)

Trial procedures summary

- Pembrolizumab 200 mg given in 3 weekly cycles until one or more protocol discontinuation criteria apply
- Radiological imaging every 12 weeks (4 cycles)
- Translational sample collection every 6 weeks (2 cycles)

End of treatment visit(30 days after discontinuation)

Follow Up if no PD on treatment (8 weekly with 12 weekly radiological imaging)

Survival Follow Up (12 weekly until death, withdrawal of consent or end of study)

6.2 Baseline Characteristics

Baseline characteristics including demographics, medical history, prior and concomitant medication, quality of life, vital signs and weight, ECOG performance status and laboratory evaluations will be summarized by cohort group using appropriate descriptive statistics.

6.3 Primary Efficacy Analysis

The overall response rate will be calculated as the proportion of patients who have a complete response (CR) or partial response (PR) to treatment as assessed by the objective tumour response criteria: RECIST v1.1 **or** immune-related (irRECIST). The response rate and its 95% confidence interval (CI) will be presented for each cohort. As previously described, the response rate is the primary efficacy variable that will be used to decide whether the study will stop or continue accrual in both cohorts.

Disease Control Rate (DCR) will be calculated for each cohort as the proportion of patients in whom the best overall response is determined as complete response (CR), partial response (PR) or stable disease (SD) for at least 12 weeks in either RECIST **or** irRECIST criteria.

The Overall Survival (OS) and Progression Free Survival (PFS) will be summarized descriptively using the median and Kaplan-Meier graph for each cohort.

The Quality of Life (QOL) in each cohort will be assessed using mean or median scores from the EORTC QLQ-C30 (version 3) questionnaire administered at baseline, after 3 months and then at discontinuation of study treatment. The QOL scores between visit dates will be compared using Repeated Measures ANOVA or Friedman's Test on the per-protocol population who completed the baseline and at least one follow-up QoL assessment. The type of statistical test to be used will depend on the characteristic of the data distribution. Adjustment for multiple testing will be applied. The Tukey post-hoc method or the Wilcoxon signed-rank test will be used for pairwise comparisons. Profile plots and longitudinal plots will also be presented.

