2.1 Primary Objectives

Objectives:

Overall response rates by immune-related (irRECIST) and RECIST criteria:

Disease Control Rate (DCR), Overall Survival (OS) & Progression Free Survival (PFS).

Hypothesis:

Pembrolizumab has Efficacy in CUP:

- as a second-line treatment in terms of Response which translates into improved PFS and OS.
- and treatment leads to rapid improvement in QOL in high metastatic disease burden.

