d Lab tests (blood samples for haematology, clinical chemistry and urinalysis) for screening should be performed within 10 days prior to the first dose of treatment. In circumstances where blood samples for haematology and clinical chemistry and urinalysis fulfils both the timeline of day -10 to 0 and 72 hours prior to C1D1 dosing these can be used for both screening and C1D1.													
eOn dosing days for all cycles, samples must be taken pre-dose (up to 72 hours prior to dosing).													
f Baseline assessment should be performed no more than 28 days before the start of study treatment and ideally as close as possible to the start of the study treatment.													
gSubsequent tumour assessments will be conducted every 12 weeks, with window for each assessment is ± 7 days.													
hTumour blocks / slides should be made available within 60 days of patient enrolment.													

4 Population of Analysis Sets

Unless otherwise stated, all analyses will be performed using the Intention-to-Treat (ITT) population which includes all study participants taking part in the trial regardless of whether they dropped out, fully adhered to the treatment or switched to an alternative treatment. A Per-Protocol (PP) population is additionally defined for the purpose of ad hoc or exploratory analyses.

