4.3 Per-Protocol (PP) Population

The Per-Protocol Population includes enrolled patients who are assessable for the primary endpoint. Assessable patients are those that have received at least 2 cycles of Pembrolizumab and are assessable for toxicity.

5 Variables of Analysis

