5.1 Primary Efficacy Endpoint

The overall response to treatment is assessed using RECIST v1.1 and immune-related (irRECIST). Appendices A and B in the protocol present the guidelines for evaluation of objective tumour response Using RECIST 1.1 (Response Evaluation Criteria in Solid Tumours) or immune-related RECIST. The disease control rate will be calculated.

Disease Control Rate (DCR) - is defined as the proportion of patients in whom the best overall response is determined as complete response (CR), partial response (PR) or stable disease (SD) for at least 12 weeks in either RECIST or irRECIST criteria.

Overall Survival (OS) - defined as the length of time from study enrolment until death, withdrawal of consent, last follow-up date if lost to follow-up or the end of the study, whichever occurs first.

Progression Free Survival (PFS) – is defined as the length of time from study enrolment to first evidence of progressive disease identified at follow-up or confirmed disease progression at the end of the trial or death. Patients will be censored at the last follow-up date if they are lost to follow-up, withdrawn from the study or have not progressed at the end of study. Median PFS and its 95% confidence interval will be reported. Kaplan-Meier survival curves will also be plotted.

Quality of Life (QOL) is measured as scores from the EORTC QLQ-C30 version 3 questionnaire which will be administered at baseline, after 3 months and then at discontinuation of study treatment.

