6.9 Withdrawal from the Study

Withdrawal can occur at any time according to the following reasons: patient decision; lost to follow-up; death, pregnancy or administrative reasons. Patients who withdraw from the study before having at least 2 cycles of Pembrolizumab or before having follow-up tumour or QoL assessment will be excluded from the Quality of Life analysis and some secondary analyses.

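### The between-visit QoL comparison is run on the per-protocol set, so early stoppers who have a baseline and a discontinuation form are dropped

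*SAP*

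**What the plan says.** Five parts of the SAP bear on this.

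- Section 4 sets the default: "Unless otherwise stated, all analyses will be performed using the Intention-to-Treat (ITT) population". It then adds: "A Per-Protocol (PP) population is additionally defined for the purpose of ad hoc or exploratory analyses".
- Section 4.3 defines the per-protocol set: "Assessable patients are those that have received at least 2 cycles of Pembrolizumab and are assessable for toxicity".
- Section 5.1 lists QoL under the primary efficacy endpoint ("Quality of Life (QOL) is measured as scores from the EORTC QLQ-C30 version 3 questionnaire"), with forms due at "baseline, after 3 months and then at discontinuation of study treatment". Section 2.1 states the matching hypothesis: "treatment leads to rapid improvement in QOL in high metastatic disease burden".
- Section 6.3, under primary efficacy analysis, first says that mean or median QoL scores will be used and names no population. It then runs the test between visits (repeated measures ANOVA or Friedman, with pairwise follow-up tests) "on the per-protocol population who completed the baseline and at least one follow-up QoL assessment".
- Section 6.9 says that patients who withdraw from the study before two cycles, or before a follow-up tumour or QoL assessment, "will be excluded from the Quality of Life analysis and some secondary analyses".

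Section 6.8 rules out imputation. No sensitivity analysis of QoL on a wider set is planned.

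**The concern.** The two-cycle condition is met or failed after treatment starts, and how the patient fares largely decides which. Patients who do not reach a second cycle are mostly those who progress, have toxicity, die or withdraw early. Because a form is due at discontinuation, some of them satisfy the other condition in 6.3, a baseline form plus one later form. Their data are collected and then set aside because treatment ended early. This is selection on outcome. It is not missing data, so the no-imputation rule does not account for it.

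At stake is the baseline-to-discontinuation change. The hypothesis is that QoL improves, and removing the patients most likely to have worsened favours it. The trial has no control arm in which the same selection would operate.

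**Working it through.** **The text.** Section 4 allows a departure from ITT where one is stated, and 6.3 states one. The ITT default is therefore not breached. The conflict is narrower: section 4 gives the per-protocol set an exploratory purpose, and 6.3 uses it for a comparison under the primary heading. Protocol 8.3 uses the same two-cycle rule for assessability but counts progression before the 12-week CT as treatment failure. SAP 4.3 does not carry that clause over.

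**Which comparisons are affected.**
- Baseline to month 3: almost unaffected, because a patient with a month-3 form will generally have had two cycles.
- Baseline to discontinuation: affected, because a one-dose patient can have both forms.
- Overall three-visit test: classical repeated measures ANOVA and Friedman need all three forms, so a one-dose patient drops out whichever set is named.

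**Size.** The documents give no QoL sample size, effect or standard deviation, so there is no plan figure to reproduce. Inputs from SAP 3.5 are PFS medians of 2 months (null) and 4 months (alternative), OS medians of 4 and 7 months, and 31 to 67 patients. SAP 3.6 gives 21-day cycles.

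Assumptions: both times are exponential; a month is 30.4375 days; a PFS event before day 21 means that dose 2 is not given; there is no other early stopping; a patient dead by day 21 has left no form.

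Formula: F(t) = 1 − 0.5^(t/median), with t = 21/30.4375 = 0.690 months.

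| | Null | Alternative |
|---|---|---|
| PFS event by day 21 | 1 − 0.5^(0.690/2) = 0.2127 | 1 − 0.5^(0.690/4) = 0.1127 |
| Dead by day 21 | 1 − 0.5^(0.690/4) = 0.1127 | 1 − 0.5^(0.690/7) = 0.0660 |
| Alive, with PFS event | 0.1000 | 0.0467 |
| Of 31 | 3.1 | 1.4 |
| Of 67 | 6.7 | 3.1 |

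**Effect on the mean.** Assume a change of +5 points in kept patients and −10 to −20 in early stoppers, with all forms returned. Among patients alive at day 21, the share of early stoppers is:
- Null: 0.1000/(1 − 0.1127) = 0.1127
- Alternative: 0.0467/(1 − 0.0660) = 0.0500

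The mean is 5 minus that share times the gap, where the gap is 15 or 25 points:
- Null: 5 − 0.1127×15 = +3.31; 5 − 0.1127×25 = +2.18
- Alternative: 5 − 0.0500×15 = +4.25; 5 − 0.0500×25 = +3.75

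The per-protocol analysis would report +5 in every case.

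**If two cycles means two completed cycles (day 42).** The shares alive with a PFS event become 0.380 − 0.213 = 0.167 and 0.213 − 0.128 = 0.085. That is 5.2 and 2.6 of 31, or 11.2 and 5.7 of 67. Among patients alive at day 42 they are 0.167/0.787 = 0.212 and 0.085/0.872 = 0.097, so the shift would be a little under double.

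**The case against.** The case on the other side is substantial, and most of it limits the point.

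- A reader might infer that QoL is analysed only in the per-protocol set. The documents do not support that. The mean and median scores in 6.3 name no population and so fall to ITT; only the between-visit test and its pairwise comparisons are restricted.
- A reader might infer that SAP 6.9 removes all early failures from QoL. Its reasons for withdrawal are patient decision, loss to follow-up, death, pregnancy and administrative reasons. Progression and toxicity are not among them. Protocol 6.9.6 lists progression and unacceptable adverse events as reasons for stopping treatment, apart from study withdrawal in 6.9.7.
- A reader might take 21% and 11% as the patients whose data are lost. On the plan's OS medians, 0.1127/0.2127 = 53% and 0.0660/0.1127 = 59% of those are deaths, which leave no form in this model.
- The remaining 10% and 5% are generous. Protocol 6.9.8 waives final-visit activities for patients too unwell to attend, the first scheduled scan is at 12 weeks, and Appendix B allows treatment past initial radiological progression.
- QoL is in the primary hypothesis but not in the listed primary objectives. It has no sample size or decision rule, and the trial summary calls the trial hypothesis generating.
- Changing the analysis set does not rescue the overall test.

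All of this stands. It does not remove the mismatch between section 4 and section 6.3, or the selection in the baseline-to-discontinuation comparison.

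**Conclusion.** The concern holds for the between-visit comparison in SAP 6.3, and in practice for the baseline-to-discontinuation contrast. Patients with both forms are excluded because treatment ended early, and the bias probably favours the QoL hypothesis. That direction is an inference, as the documents contain no QoL data.

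If two cycles means that dose 2 was given, at most about 10% (null) or 5% (alternative) of patients could be restored. The resulting shift is about 1.7 to 2.8 points (5 − 3.31 and 5 − 2.18) or 0.75 to 1.25 points (5 − 4.25 and 5 − 3.75). It depends on exponential times and on the assumed changes of +5 and −10 to −20. Within that model it is an upper bound, since some early stoppers will be too unwell to complete a form. Stopping for toxicity or by choice before dose 2, or the completed-cycle reading, would increase it. No stated trial decision rests on QoL, so this should be corrected but does not undermine the design.

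**What to change.** In SAP 6.3, define the main QoL comparison on all treated patients with a baseline form and at least one later form, the discontinuation form included, whatever the number of cycles. Name a method that keeps patients with incomplete visits, such as a mixed model for repeated measures using actual assessment times. At the least, run the paired baseline-to-discontinuation comparison on all available pairs. Keep the per-protocol result as a sensitivity analysis, which fits section 4.

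Amend 6.9 so that withdrawal before two cycles no longer removes a patient who has the required forms. State whether two cycles means doses given or cycles completed. Report form completion by visit, with reasons for missing forms, because patients who die or are too ill to respond stay unobserved under any set.

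The cost is SAP wording and a little analysis work, with no new data collection. The QoL result may be less favourable.
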